21.2.4 Other assessments

21.2.4.1 MRI parameters

In addition to ASL, we propose to explore the changes in the behaviour over time of conventional and advanced imaging measures, which may be influenced by the effects of simvastatin.

We will combine the well-established imaging measures that reflect both neurodegeneration, such as brain grey matter atrophy, and neuro-inflammation, such as the number of new or enlarging T2 lesions, with novel measures (i.e., NODDI-derived measures and myelin maps), that have potential to detect more specific neuro-axonal abnormalities and metabolic changes, and any effects of simvastatin.

These novel markers may provide complementary information to that given by the retinal microvascular study, ASL and clinical measures (see statistical paragraph below for a comment on the role of these measures).

(1) Diffusion weighted imaging (DWI) is an MR imaging technique based upon the measurement of the random Brownian motion of water within a voxel of tissue. This technique has been used to analyse the microstructure of neuronal tissue in particular myelin and axonal integrity. Multi-shell DWI acquisition allows the use of several multi-fibres and multi-shell modelling approaches, such as Diffusion Kurtosis Imaging (DKI) and Neurite Orientation Dispersion and Density imaging (NODDI), which have been successfully used to study patients with MS. It has been demonstrated that NODDI has higher sensitivity and specificity than standard Diffusion Tensor Imaging (DTI).

(2) Macromolecular tissue volume (MTV) is a method of myelin mapping to determine the role of myelin loss or changes in progressive MS. With the macromolecular volume being made up of 50% myelin, we are able to use an in-house analysis pipeline to calculate the MTV - a surrogate marker of brain myelin volume. This metric, alongside diffusion weighted imaging will provide micro-structural detail into the cross-sectional and longitudinal changes occurring in the brain parenchyma of people with progressive MS.

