21.2.4.4 Retinal Imaging Metrics

(1) Vascular imaging: adaptive optics and scanning light ophthalmoscopy (AOSLO) of retinal capillary microvessels (Dubra and Sulai, 2011; Sulai et al. 2014). This enables us to calculate retinal perfusion and measure blood flow dynamics at the capillary level. We will measure vein and arteriole wall thicknesses and erythrocyte occupancy in the capillaries. We will also look at how flow changes between resting and retinal stimulation (Zhong et al, 2008). Briefly, this will be accomplished by flashing a dim light and looking

at how blood cell movements change and vessel walls expand. Metrics will be occupancy before and after stimulation and vessel width before and after flashing.

(2) Relative retinal vessel oxygen saturation and vessel width: using the Oxymap T1 installed on a conventional Topcon fundus camera we will be able to measure relative venous and artery blood pO₂ levels near the optic nerve (central 3 disk diameters).

(3) Non-invasive wide-field maps of both retinal (superficial and deep) and choroidal vascular plexuses: using optical coherence tomography angiography (OCTA) vessel density and organisation (fractal dimension) will be assessed.

(4) Spectral-domain OCT (SDOCT): to evaluate retinal lamination, total retinal thickness, inner retinal thickness (including RNFL thickness), outer retinal thickness and the inner and outer segment lengths.

22. Sample size and recruitment

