22.1 Sample size calculation

The power calculation (N=20 subjects per arm) is based on the ability to detect a 30% change in perfusion induced by statins at 0.8 power and 5% significance level. An expected mean grey matter CBF of 40 mL/100g per min and a standard deviation per subject of 12 mL/100g per min were chosen leading to N=17 per group. Accounting for drop-outs and problems in imaging patients (e.g. motion artefacts (20%) gives N=20 subjects per group. A hypothetical increase in CBF by 30% was estimated based on a previous paper comparing the effects of normal doses of statins on healthy volunteers (Xu et al., 2008). Any potential regression to the mean, which was not accounted for above will lead to a lower number of subjects per arm being necessary.

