22.3 Randomisation methods

This study will have a participant randomised design with equal allocation between treatment arms. Randomisation with a minimization algorithm will be used, using up to a maximum of four binary variables:

- gender

- binary age (≤ 55 />55 years old)
- binary disability (EDSS ≤ 5.0 />5.0)
- binary progressive clinical phenotype (SPMS/PPMS)

The cut-offs have been decided based on the literature: an age ≤ 55 years old was part of the inclusion criteria for the ORATORIO trial (ref: Montalban et al., NEJM 2016); in the same trial an EDSS score of 5.0 or lower was considered as 'less disabled', for which shorter disease durations were assumed/required to enter the trial (ref: Montalban et al., NEJM 2016). The study is exploratory and the number of subjects/arm is estimated based on established measures of within and between subject standard deviations using ASL, based on a large test-retest study (Petersen et al., 2010).

Randomisation will be performed by the PI or delegated member of the clinical investigating team at local sites using the web-based randomisation service, Sealed Envelope. A random sequence for study arm allocation will be computer generated by Sealed Envelope providing a unique trial identification code for each recruited participant.

Eligibility and consent will be verified before each patient is randomised. Study arm allocation into two treatment arms (1:1) will take into consideration these minimisation factors:

Randomisation with minimisation will ensure comparability of the two study arms, and prevent selection bias.

[figure not shown]
Sealed Envelope will generate unique identifiers for every active/placebo drug kit. The drug kit identification codes will be provided to Sealed Envelope and the Qualified Person (QP) at drug manufacturing site (Mode Pharma) who will ensure that trial drug and placebo packs are labelled appropriately, and that the trial team and participants remain blind to treatment allocation. At baseline, the investigator will enter the patient's unique trial identification code into the SealedEnvelope.com website which will then provide the drug identification code of the active/placebo drug kit to be dispensed. Sufficient number of simvastatin/placebo drug kits will be provided to ensure availability of adequately labelled kits for Pharmacy dispensing.

23. Statistical analysis plan

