- To collect health economic data (EQ5D5L) to inform future phase III trials.

- **Exploratory objectives:** to advance our understanding of the mechanisms of efficacy, and how vascular perfusion and oxidative damage is affected in progressive MS both in the presence and absence of simvastatin.

- To investigate phenotypic immune markers in whole blood to determine effect simvastatin has on immune function.
- To measure biomarkers of blood brain barrier dysfunction, vascular leakage and oxidative damage in participants treated with statins and placebo.
- To investigate levels of circulating cholesterol.

2. Statistical Analysis Plan:

- **Primary outcome analysis.** The ASL-measured CBF in white matter (), grey matter, deep grey matter, and thalamus will be compared between patients on simvastatin or placebo using *multiple linear regressions* at 16 weeks as the dependent variable, and age, gender or CBF at baseline and treatment group entered as covariates. Whenever the variable ‘treatment group’ is significant (at 5% significance level), it will be assumed that there is a treatment effect. The same models will be used to investigate the effect of simvastatin on the other imaging outcome measures.
- **Checks for model assumptions.** For all regression-type approaches, we will assess the normality of the residuals (of each one of the fitted models) through q-q plots. Residual homoscedasticity will be assessed through two-way scatter plots of the residuals over fitted values. Once we build the model with all possible predictors as explanatory variables, the assumption of the linear relationship between the dependent variable and each one of the predictors individually, given the presence of the other predictors, will be assessed through investigating different functional forms of the predictor and their impact on the R2 of the model. The independence of observations will be always assumed.
- **Violations of model assumptions.** If the main assumption violated is that of homoscedasticity (i.e. there is residual heteroscedasticity), robust estimations of the standard errors (SE) of the regression parameters will be made, using the sandwich estimator of the SE. Whenever the residual distributions show a clear deviation from normality, bootstrap-based approaches will be used, with at least 1000 replication samples: bias-corrected and accelerated bootstrap-based 95% Confidence Intervals (95% CI) will be computed for each estimated parameter.

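### The rule that a 5%-significant treatment term is taken as a treatment effect carries over, on its natural reading, to the other imaging outcomes, with no error control and against the plan's own exploratory wording

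*SAP*

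**What the plan says.** The primary-outcome paragraph of SAP section 2, matched by protocol 23.3, fits a linear regression to 16-week CBF with treatment group as a covariate. It adds that whenever the treatment term "is significant (at 5% significance level), it will be assumed that there is a treatment effect". The next sentence extends the approach: "The same models will be used to investigate the effect of simvastatin on the other imaging outcome measures". The other imaging outcomes are neither listed nor counted there.

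They have to be gathered from protocol section 21:

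- **MRI.** Sections 21.2.1 and 21.2.4.1 name total, regional and thalamic grey matter volumes, new or enlarging T2 lesions and new T1 hypointense lesions. These are combined "with novel measures (i.e., NODDI-derived measures and myelin maps), that have potential to detect more specific neuro-axonal abnormalities and metabolic changes, and any effects of" the study drug.
- **Retina.** Section 21.2.4.4 lists AOSLO, Oxymap and OCT-angiography metrics, and spectral-domain OCT "to evaluate retinal lamination, total retinal thickness, inner retinal thickness (including RNFL thickness), outer retinal thickness and the inner and outer segment lengths".

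No hierarchy, alpha adjustment or false-discovery rule for these outcomes appears in either document.

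Exploratory wording does appear in other places. Protocol 22.3 and the trial summary call the study exploratory. Protocol 21.2.4.1 proposes to explore the MRI measures. The heading of protocol 23.4 groups secondary with other exploratory analyses. The SAP's atrophy and advanced-MRI aims, though filed as secondary, are both phrased as aims to explore.

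**The concern.** A rule that turns any p<0.05 into an assumed effect is tolerable for one pre-specified test. Applied outcome by outcome to a long, unlisted set of measures in 40 patients, it lets chance alone produce a declared effect far more often than 5% of the time.

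The trial is meant to show how simvastatin might work: through perfusion, or through neuro-axonal, myelin or retinal changes. A spurious secondary finding would steer that conclusion. It could also carry forward, because the SAP says the data on these MRI parameters can be used to power later neuroprotective trials.

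This point covers only the other imaging outcomes. It does not concern the several CBF regions within the primary analysis or the association models in the exploratory paragraph.

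**Working it through.** **Test level.** The documents state no family-wise error rate, so there is no such figure to reproduce. The sample size does indicate the sidedness of the 5%. Protocol 22.1 aims to "detect a 30% change in perfusion induced by statins at 0.8 power and 5% significance level", and "An expected mean grey matter CBF of 40 mL/100g per min and a standard deviation per subject of 12 mL/100g per min were chosen".

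- Difference: 30% of 40 = 12. SD = 12. Standardised effect = 12/12 = 1.0.
- Normal approximation, two-sided: n = 2 × (1.960 + 0.842)² / 1.0² = 15.7, so 16 per arm.
- With the t distribution: 16.7, so 17 per arm, which is the stated N=17.
- One-sided 5% (normal approximation) would give 13.

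The stated N=17 therefore fits a two-sided 5% test, and that is used below.

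**Count of outcomes (an assumption: one value per named metric).**

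- MRI, 8: whole-brain atrophy, total grey matter volume, thalamic volume, neurite density, one further NODDI measure, MTV, new or enlarging T2 lesions, new T1 lesions.
- Retinal, 19: AOSLO 4 (vein wall, arteriole wall, erythrocyte occupancy, vessel width); Oxymap 3 (arterial and venous saturation, vessel width); OCT angiography 6 (density and fractal dimension in three plexuses); spectral-domain OCT 6.
- Total: 8 + 19 = 27. Regional volumes, or week-20 comparisons, would add more.

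**Chance of at least one declared effect when simvastatin is inert.**

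Independent tests: 1 − 0.95^k.

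- k = 8: 1 − 0.663 = 33.7%.
- k = 27: 1 − 0.250 = 75.0%.

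For a common correlation ρ between test statistics, condition on one shared normal factor c and integrate:

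1 − ∫ φ(c) [Φ((1.96 − √ρ·c)/√(1−ρ)) − Φ((−1.96 − √ρ·c)/√(1−ρ))]^k dc

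| Outcomes tested | ρ = 0 | ρ = 0.5 | ρ = 0.8 |
|---|---|---|---|
| 5 (a shorter MRI list) | 23% | 18% | 13% |
| 8 (MRI) | 34% | 25% | 16% |
| 27 (MRI and retinal) | 75% | 48% | 25% |

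At ρ = 0.3 the 27-outcome figure is 63%. The documents give no correlations, so the range is shown rather than one value.

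Expected number of false declarations, whatever the correlation: 8 × 0.05 = 0.40 for MRI and 27 × 0.05 = 1.35 for the full set.

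**When does a false declaration become more likely than not?** With independent tests, k = 13 gives 48.7% and k = 14 gives 51.2%, so at least 14 are needed. At ρ = 0.5, even 28 tests give 49.2%.

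**Check of the optional adjustment.** Simulated Benjamini-Hochberg at 5%, all nulls true, 7 to 25 tests and correlations 0 to 0.8, gave any positive result in 2.4% to 5.1% of runs. List sizes of 8 and 19 lie within that range. With two separate lists the combined chance is at most about 1 − 0.95² = 9.8% if the lists are independent.

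**The case against.** The strongest reply is that a 40-patient mechanistic phase II trial need not adjust its secondary outcomes, and that the documents already signal caution. They call the study exploratory, phrase the MRI aims as exploration, and concede that numbers may be too small to show significance on such measures. This stands in part: formal adjustment here is a debatable choice, not an obligation. A reader might infer that the imaging outcomes carry no exploratory label at all, and the documents do not support that. What is missing is any such qualification at the decision rule, which as worded contradicts it.

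Second, the text extends the models, not in so many words the rule, and the rule sits under the primary outcome. That is correct, so the carry-over is the natural reading and not explicit text. But for the secondary MRI outcomes no other rule for judging a treatment effect is given. The SAP's secondary-outcome paragraph deals only with retinal metrics, and its neurite-density estimate (13 per arm, 80% power) speaks of seeing a significant treatment effect.

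Third, that same paragraph gives retinal imaging its own approach, with normative controls and unspecified multigroup tests. Whether the 19 retinal metrics fall under the rule is therefore uncertain, and the 27-outcome row is conditional on it. Some counted items are also loosely defined: the second NODDI measure is not named, and retinal lamination is not a defined single value. New-lesion counts have no baseline value to adjust for, so the same model cannot be applied to them literally.

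Fourth, independence is implausible for nested measures. Inner retinal thickness includes the RNFL, and thalamic volume is listed within the grey matter volumes. This stands, and is why the correlated figures are given.

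**Conclusion.** The point holds in a bounded form. Followed on its natural reading, the plan would declare at least one spurious imaging effect in about 16% to 34% of null trials from roughly 8 MRI outcomes. Even a list of five gives 13% to 23%. If the retinal metrics are covered as well, the range is about 25% to 75%. The lowest figure for the 8 MRI outcomes is about three times the stated 5%. All figures assume two-sided 5% tests, every null true, one value per metric and a common correlation between 0 and 0.8.

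A reader might conclude that the trial would probably declare a false imaging effect. The documents do not support that. A chance above one half needs at least 14 nearly independent tests, so it requires the retinal metrics to be covered and weakly correlated. It does not hold for the MRI outcomes alone, nor for all 27 at a correlation of 0.5 or more. What is firm is that the decision rule conflicts with the exploratory wording used elsewhere and leaves the error rate for these outcomes uncontrolled.

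**What to change.** In SAP section 2 and protocol 23.3:

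1. Limit the sentence that assumes a treatment effect from a 5%-significant term to the primary CBF analysis.
2. State that the other imaging outcomes are hypothesis-generating, reported as adjusted differences with 95% confidence intervals, and that no treatment effect will be concluded from an unadjusted p-value.
3. Say whether the retinal metrics use these models or the separate multigroup tests.
4. Only if a claim on a secondary imaging outcome is wanted, list the MRI and retinal outcomes in advance and apply Benjamini-Hochberg at 5% within each list. The lists are essential, since the procedure cannot be applied to an open set.

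This takes a few sentences in each document and needs no new patients or data. The downside is that an isolated p<0.05 on a secondary imaging measure can no longer be called a treatment effect.

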- **Secondary outcome analysis.** Metrics for quantifying blood flow from retinal imaging are in development, and have not previously been applied in MS patients. Retinal vessel walls will be assessed in a similar fashion to that outlined by Chui et al (2013). Arterial wall thickness will be assessed as a function of lumen thickness. In the first instance normative data will be obtained from age-matched controls prior to imaging patients with MS. Subsequently appropriate multigroup statistical tests will be applied. Capillary network density will be assessed using similar methods to those described by Tam et al. (2010) and blood velocity will be calculated building up spatio-temporal analysis outlined by Tam et al. (2011).
- **Exploratory analyses.** Exploratory analyses will be performed to assess the associations between ASL changes (dependent variable) and all secondary outcome measures (explanatory variables). An interaction term such as ‘secondary outcome measure change’ X ‘treatment group’ will be included in the model as an explanatory

variable. Whenever it becomes significant it will indicate that simvastatin influences the association between primary and secondary outcome measures.

Although the sample size of this study was based on the ASL, we estimated that the number of patients that we would need to detect an increase in neurite density of 0.128 that represents a 20% treatment effect (Magnollay et al., 2013) would require 13 per arm (80% power). Additionally, even if the number of patients per arm will not be sufficient to see a significant treatment effect of this size, this study will provide information on the temporal behaviour of these MRI parameters that can be used to power future neuroprotective trials.

Model assumptions will be also checked as described above and any violations of the model assumptions will be dealt with in a similar way.

- **Sensitivity and other planned analyses.** Baseline clinical, demographical and neuroimaging characteristics of those patients with missing visits will be compared with those of patients without missing values, to investigate the assumption of missing at random (MAR). If there is no evidence against MAR, multiple imputation methods will be performed, and any serious discrepancy between the complete case results and the imputation results will be reported. Worst- and best-case sensitivity analyses will also be performed.

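### The exploratory ASL association analysis reads any significant change-by-treatment interaction as a simvastatin effect, with the model unspecified, no multiplicity control and no baseline CBF

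*SAP*

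**What the plan says.** SAP section 2, Exploratory analyses, sets out to assess "associations between ASL changes (dependent variable) and all secondary outcome measures (explanatory variables". A term multiplying the change in a secondary measure by treatment group "will be included in the model as an explanatory" variable. The reading rule follows: "Whenever it becomes significant it will indicate that simvastatin influences the association between primary and secondary outcome measures". Protocol 23.4 has the same rule.

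The text does not state:
- whether there is one joint model or one per measure;
- which covariates enter, including the treatment main effect;
- over which interval change is measured (MRI is scheduled at baseline, week 16 and week 20);
- the significance level, the number of tests, any multiplicity control, or power for the interaction.

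The primary model, by contrast, lists "age, gender or CBF at baseline and treatment group entered as covariates", and its rule is "Whenever the variable ‘treatment group’ is significant (at 5% significance level), it will be assumed that there is a treatment effect". The 5% level is stated there and is not repeated for the interaction.

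**The concern.** The rule turns each nominally significant interaction into a statement about what simvastatin does. Applied to a long list of measures in a small trial, it will often give such a statement by chance, and a moderate real difference between arms will usually be missed.

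The interaction is also not protected by randomisation in the way the primary comparison is. The secondary-measure change on the explanatory side is itself observed after randomisation, so a difference in slopes does not by itself identify a drug effect on the association.

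Leaving out baseline CBF discards precision that the trial has already paid for.

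At stake is the reporting of the association aims, including the SAP aims on how ASL relates to AOSLO flow and to retinal nerve fibre structure on and off treatment. The primary result is not affected.

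**Working it through.** **Sample size.** Protocol 22.1 takes a mean grey matter CBF of 40, a 30% change and an SD of 12 mL/100g per min. The difference is 0.30 × 40 = 12, so d = 12/12 = 1.0. A two-sample t-test at two-sided 5% and 80% power needs 16.7, so 17 per arm, which matches "standard deviation per subject of 12 mL/100g per min were chosen leading to N=17 per group". I use 17 per arm, 34 in all. A literal 20% loss from 20 per arm leaves 20 × 0.8 = 16, slightly worse than assumed here.

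**Number of measures, K (assumption).** The protocol's structured summary, at one metric per item, gives 4 MRI + 8 clinical, patient-reported and health-economic + 6 retinal = 18. Splitting out some of the metrics in Protocol 21.2 gives 6 MRI + 8 clinical + 10 retinal = 24. FAB is scheduled only at baseline and week 20, so it has no week-16 change. Without it the lower count is 17.

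**Joint reading.** Coefficients = intercept + treatment + K changes + K interactions = 2K + 2.
- K = 17: 36
- K = 18: 38
- K = 24: 50

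All exceed 34. If all 40 randomised patients were complete, K = 18 would leave 40 − 38 = 2 residual degrees of freedom.

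**One measure per model: false claims.** If no true interaction exists, the expected number of false ones at 5% is 0.05K: 0.9 for 18 and 1.2 for 24. For independent tests, P(at least one) = 1 − 0.95^K:
- K = 17: 58%
- K = 18: 60%
- K = 24: 71%

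Simulated regressions (intercept, treatment, change, interaction; 17 per arm; one CBF region) agree to within simulation error. When the measures correlate 0.6 with each other, the chance falls to about 35–37% for 18 measures and 40–43% for 24. The SAP names four CBF regions, and using each would raise the chance further.

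**Power for one real interaction.** The effect sizes are assumptions: correlation r on simvastatin, 0 on placebo. By Fisher's z, power ≈ Φ(atanh(r)/√(2/14) − 1.96), where 14 = 17 − 3.

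| r v 0 | atanh(r)/√(2/14) | Power, Fisher z | Power, simulated regression |
|---|---|---|---|
| 0.3 | 0.82 | 13% | 12% |
| 0.5 | 1.45 | 31% | 29% |
| 0.7 | 2.29 | 63% | 55–56% |

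**Baseline CBF.** Assume equal SDs at baseline and follow-up, with correlation r between them. Change then correlates with baseline at −√((1 − r)/2): −0.50 for r = 0.5 and −0.39 for r = 0.7. Adjusting for baseline leaves a residual variance of (1 − r²)/(2(1 − r)) = (1 + r)/2 of the change-score variance: 0.75 for r = 0.5 and 0.85 for r = 0.7. If the 0.5 v 0 difference lies in the part of follow-up CBF that baseline does not explain, simulated power rises from about 22–26% unadjusted to about 27–30% adjusted. The unadjusted figure is below the 29–31% above because there the 0.5 was set on the raw change itself.

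**The case against.** The strongest reply is that these analyses are labelled exploratory, in a study the protocol itself calls exploratory, and that the SAP applies its residual checks and sandwich or bootstrap remedies to these models too. The label does permit many analyses without strict error control. It does not cover a sentence that converts each significant result into a statement about simvastatin, and the model checks do nothing about the number of tests.

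It can also be said that omitting baseline CBF costs precision and does not bias the interaction. That stands: baseline adjustment is a modest gain. Once baseline is a covariate, week-16 CBF and change give the same interaction coefficient, so the outcome need not be switched.

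A reader might infer several stronger points that the documents do not support:
- **The analysis cannot be fitted at all.** The interaction term is described in the singular and the SAP elsewhere speaks of each fitted model, so one model per measure is an equally natural reading. The defect is that the plan does not say which.
- **A false claim is likelier than finding a real effect.** That compares the error over a whole set of tests with the power of a single test. Any single test has a 5% false-positive rate, below its power in every case shown.
- **Unequal spread of CBF change between arms creates spurious interactions.** With equal correlation and a 1.5-fold SD in one arm, the slopes truly differ, because slope = correlation × SD ratio. Rejection of 9–19% there is detection of that difference. With equal slopes and unequal residual spread, rejection stays at about 5%.
- **The mechanism question rests on this model.** CBF and the other imaging outcomes are compared between randomised arms in the primary-type models.

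**Conclusion.** The concern holds in a limited form. The plan leaves the exploratory model unspecified, sets no control for the number of tests, and states a reading rule stronger than the analysis can bear. With 18–24 measures, one per model, one CBF region and 17 per arm, the rule would produce at least one false statement about simvastatin in about 35–70% of trials when no interaction exists. A moderate real interaction (0.5 v 0) would be missed about 70% of the time.

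These figures rest on assumptions that are not in the documents: the count of measures, the correlation between them (0 to 0.6), the size of a real interaction, and a 5% level carried over from the primary analysis. Read as one joint model, the analysis cannot be fitted with the planned 34 evaluable patients even at the lower count. The omission of baseline CBF is a smaller point about precision.

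This should be corrected before the analysis is run. It does not touch the primary comparison.

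**What to change.** Amend the exploratory paragraph of SAP section 2, and note the change against Protocol 23.4:

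1. State one secondary measure per model, with treatment, the change in the measure and their interaction. Define the change interval and list the measures that have data at both ends of it.
2. Add baseline CBF as a covariate.
3. Report the slope in each arm and the difference in slopes, with 95% CI.
4. Replace the reading rule with a statement that interactions are hypothesis-generating, are not randomised contrasts, and are reported with the total number of tests and false-discovery-adjusted q-values. Bonferroni over 18 tests would leave about 6% power for 0.5 v 0, so it is not a useful substitute.

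The SAP aims list both AOSLO and retinal nerve fibre measures as correlates, so the documents give no ground for this review to single one out as the key association. The sponsor may do so if it wishes.

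The cost is wording only, with no new data. The downside is that fewer associations can be presented as positive findings.

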23.2 Statistical Analysis Plan

The stats analysis plan will be produced well in advance of seeing the data. It will specify both the primary analysis (in detail) and the secondary analyses (in less detail), including details of the analysis methods and any pre-specified covariates for adjustment such as the minimisation variables. It will also provide details of adverse events analyses and per-protocol analysis using adherence information. The analysis plan will describe contingency analysis should the assumptions of the primary methods not be satisfied by the data. A CONSORT flow diagram will be produced.

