In general, given that we will use randomisation with minimisation, we do not expect major imbalances at baseline. However, should there be any, we will consider adjusting the models for the imbalanced variable.

- **Interim analysis.** Due to the short-term nature of the study and small sample size, an interim analysis will not be required.

3. CONSORT 2010 Flow Diagram

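### Multiple imputation depends on a baseline comparison that can speak against MCAR but cannot test MAR

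*SAP*

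**What the plan says.** The SAP's paragraph on sensitivity and other planned analyses has four steps.

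1. Clinical, demographic and imaging variables at baseline, for patients with missing visits, "will be compared with those of patients without missing values, to investigate the assumption of missing at random (MAR").
2. "If there is no evidence against MAR, multiple imputation methods will be performed".
3. After imputation, "any serious discrepancy between the complete case results and the imputation results will be reported".
4. "Worst- and best-case sensitivity analyses will also be performed". This step does not depend on the first.

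Protocol 23.5 gives the same rule and adds an analysis of missingness patterns, with no method. Neither document states a test, a threshold or an imputation model, or defines worst and best case for a continuous outcome.

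The SAP's primary model for week-16 CBF has "age, gender or CBF at baseline and treatment group entered as covariates". I read this as age, gender and baseline CBF together, as in the protocol's structured summary (2.1). Protocol 22.3 minimises on gender, age, EDSS and progressive phenotype, and Protocol 23.2 says the SAP will give "any pre-specified covariates for adjustment such as the minimisation variables". EDSS and phenotype are not in the SAP's model.

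**The concern.** The rule attaches the wrong label to the check. MCAR means that missingness is unrelated to any data, so a baseline difference between patients with and without missing visits is evidence against it. MAR means that missingness may depend on observed data but not, given those data, on the unobserved values. A baseline difference fits MAR well and identifies variables that the imputation model should contain. Whether missingness also depends on the unseen week-16 CBF cannot be settled from observed data.

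Taken literally, a clear baseline difference could be read as evidence against MAR and imputation dropped, in the situation where imputation using those variables is most useful. The planned comparison of complete-case and imputed results would be lost with it. An undefined judgement, made after the data are seen, would decide whether that comparison is produced.

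**Working it through.** **Inputs from the documents.** N=40, 20 per arm (Protocol 2.1). Protocol 22.1 allows 20% for drop-out and imaging problems, so 0.20 × 40 = 8 patients. It needs 17 evaluable of 20, so 3 of 20 (15%) or 6 of 40 is the lower figure. The plan gives no figure of its own for the missing-data rule to reproduce. Everything below that concerns a test assumes a 5% two-sided t-test.

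**1. What the comparison responds to.** Simulation: N=40, about 20% missing, baseline-outcome correlation 0.6, logistic missingness slope 1.5 per SD, 4,000 trials per mechanism (all assumed). The last column is the bias of a regression-based, MAR-valid estimate of the outcome mean.

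| Mechanism | Comparison significant | Bias (SD) |
|---|---|---|
| MCAR | 5.2% | 0.00 |
| MAR, driven by baseline | 85% | 0.01 |
| MNAR, driven by the part of the outcome unrelated to baseline | 5.1% | -0.18 |

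The comparison flags the case where MAR methods work and treats this MNAR case like MCAR.

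**2. Missingness driven by week-16 CBF itself.** The baseline imaging variables include baseline CBF, so some of this dependence shows. With correlation 0.5, slope 1.0 to 1.5 per SD and 20% loss, a test on baseline CBF is significant in 19 to 29% of trials when the mechanism acts in both arms. With loss in the active arm only it is 11 to 15%. Chance is 5%. The comparison sees outcome dependence only as far as the outcome correlates with baseline.

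**3. Power.** Noncentral t for a baseline difference of 0.5, 0.8 or 1.0 SD:
- 8 v 32 patients: 23%, 51%, 69%
- 6 v 34 patients: 20%, 42%, 60%

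Absence of a significant difference is therefore weak evidence of anything.

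**4. How often the condition could fail under pure MCAR.** If any p<0.05 among k independent characteristics counts as evidence, the chance is 1 - 0.95^k:
- k=5: 1 - 0.774 = 22.6%
- k=10: 1 - 0.599 = 40.1%
- k=15: 1 - 0.463 = 53.7%

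Simulation with 8 of 40 missing and mutual correlation 0.3 gives 21%, 35% and 46%. The value k=15 counts EDSS, 25FTW, 9HPT, SDMT, FAB, MSIS-29v2, MSWSv2 and EQ5D5L (Protocol 9.2), age, gender and phenotype (22.3), and CBF in four regions (SAP): 8 + 3 + 4 = 15.

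**5. Why deleting the condition is not enough.** If only week-16 CBF is missing, patients without it add nothing to a regression on the primary-model covariates, so imputing from those covariates returns the complete-case answer. Simulation: true effect 0, SD 12, 21% active-arm loss driven by an EDSS-like variable outside the model, no placebo loss, four assumed strengths. Bias in mL/100 g/min:
- complete case: -0.44, -0.52, -0.81, -1.11
- imputation without the variable: -0.44, -0.52, -0.81, -1.12
- imputation with the variable: 0.00, 0.07, 0.05, 0.06
- complete case with the variable added: -0.01, 0.05, 0.01, 0.03

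**The case against.** Only imputation is conditional. The complete-case result and the worst- and best-case analyses are produced in any event, so the fallback is implied. This stands, and it limits the point to one sensitivity analysis. The protocol's missingness-pattern analysis is also unconditional, but it cannot test MAR either.

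A statistician may judge the baseline comparison as a whole and not by p-values. The documents set no 5% rule, so the rates in step 4 are illustrations, not properties of the plan. The group compared may also be smaller than 8: the check names patients with missing visits, and a patient whose scan is spoiled by motion has attended. Both objections stand.

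Three stronger readings are tempting.

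- A reader might infer that outcome-dependent missingness is wholly invisible to the check. Step 2 shows otherwise, because imaging variables are among those compared.
- A reader might charge the rule with allowing imputation where it is invalid. It can, but no rule based on observed data prevents that, and always imputing allows it in every trial.
- A reader might take the biases in step 5 as the harm done by the rule. They come from the covariate left out of the primary model. They require missingness that depends on it differently by arm, which the documents do not suggest, and adding it to the complete-case model removes them. With the same mechanism in both arms at 20% loss, the bias is at most 0.06.

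**Conclusion.** The condition is wrong as worded: it treats evidence against MCAR as evidence against MAR. That follows from the definitions and needs none of the assumed settings. The consequence is that imputation, and the planned comparison with the complete-case result, may be withheld where it is valid and most informative. The primary estimate is unaffected, and the documents do not support a claim that the rule biases it.

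How often this would happen cannot be read from the documents. The 21 to 54% under MCAR rests on the any-p<0.05 reading, 5 to 15 characteristics and 8 of 40 patients missing. It shows a noisy condition, not a biased result. The unstated imputation model and the undefined worst and best cases are part of the same small gap. Severity: minor.

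**What to change.** 1. Delete the conditional clause in the SAP and in Protocol 23.5. Always report multiple imputation beside the complete-case result when week-16 CBF is missing.
2. State the imputation model: arm, the primary-model covariates, and baseline EDSS and phenotype, which are the remaining minimisation factors. Say whether week-20 CBF, measured after treatment ends, is an auxiliary variable.
3. Keep the baseline comparison as a description of what predicts missingness.
4. Because always imputing gives no protection against MNAR, define the worst- and best-case analyses as prespecified shifts of the imputed week-16 CBF, by arm. The sponsor's statistician should choose the size. The estimate moves by about the shift times the fraction imputed in that arm. As an illustration only, a shift of one design SD (12) moves it by 12 × 0.15 = 1.8 to 12 × 0.20 = 2.4 mL/100 g/min.

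The cost is wording in two documents and no new data. Protocol 23.7 already provides for describing and justifying such a change in the protocol or the final report.
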